**Comparison of Vibrating Mesh Nebulizer versus Jet Nebulizer in the
Pediatric Asthma Patient a Randomized Controlled Trial**

NCT02774941

2/15/19

**The University of Texas Southwestern Medical Center at Dallas
Institutional Review Board**

Title:

Comparison of Vibrating Mesh Nebulizer versus Jet Nebulizer in the Pediatric Asthma Patient a Randomized Controlled Trial

Principal Investigator:

[name] RRT-NPS, Clinical Research Coordinator – Respiratory Care Department, Children's Medical Center - Dallas

1. Introduction and Purpose:

The purpose of this study is to compare clinical outcomes related to our current practice of using a jet nebulizer (JN) with aerosol mask (AM) or mouthpiece (MP) versus a vibrating mesh nebulizer (VMN) with a valved-mask (VM) or MP in the treatment of acute moderate to severe asthma in Children's Medical Center Dallas Emergency Department (CMCED). We hypothesize that using the combination of a VMN and VM or MP will result in fewer hospital admissions, treatments and length of stay in CMCED when compared to our current practice of using a JN and AM or MP.

2. Background:

Inhaled β -agonists are the treatment of choice for patients presenting in the emergency department for acute asthma exacerbation[1-4]. There are different types of aerosol delivery devices and patient interfaces available to administer therapy. JN's and metered dose inhalers (MDI) are commonly used as the main aerosol delivery device in treatment of acute asthma in pediatric patients. A mouthpiece or mask may be used as a patient interface for either device. Interface selection is usually based on patient size, age, compliance, or availability of stocked product.

Current recommendations for the initial treatment of moderate to severe asthma in the emergency department are to administer three β -agonist treatments over 1 hour in 20 minute increments or one treatment continuously over an hour [1, 4]. MDI's or nebulizers can be used to administer intermittent therapy but nebulizers must be used to deliver continuous treatment. Current data suggest continuous nebulized albuterol (CNA) reduces hospital admissions and offers time savings in the delivery of asthma therapy when compared to intermittent treatments.[5, 6] Mouthpieces deliver more aerosolized medication than aerosol masks but it is difficult for children to hold and seal the mouthpiece between their lips for 1 hour during continuous therapy.[7]

VMN's are more efficient and deliver higher concentrations of medication in simulated lung models when compared to JN's.[7-10] In a recent simulated lung model study the combination of a VMN and VM delivered significantly more medication than a JN with AM, and when VMN was used with a mouthpiece there was almost an 8 fold increase in drug delivery.[7] Further studies are needed to assess the clinical efficacy of delivering higher dosages.

3. Concise Summary of Project:

This study will compare clinical outcomes of using a JN with AM or MP versus VMN with VM or MP in the treatment of acute moderate to severe asthma in CMCED. Patients will be treated according to CMCED's current Acute Asthma Clinical Pathway Algorithm for ED (AACPA) and randomized to receive aerosol therapy via JN with AM or MP (control group) or VMN with VM or MP (study group). Study personnel will screen CMCED census through the EMR for patients diagnosed with acute asthma exacerbation with an initial assessment of moderate to severe asthma (AS 5-12), according to the AACPA. Study personnel will approach the parents for study consent as soon as possible after CMCED admission and before any bronchodilator treatment begins. We are evaluating nebulizer devices in this study. Investigators and treating physicians will be blinded to which nebulizer was assigned to each patient. Primary study outcomes will be hospital admission rates. Secondary study outcomes will be number of treatments and length of stay in CMCED.

4. Study Procedures:

Upon admission to CMCED patients diagnosed with acute asthma exacerbation will receive an initial assessment and asthma score (AS), per the AACPA. Patients assessed with moderate to severe asthma exacerbation (Moderate; AS 5-8, Severe; 9-12) will be eligible for enrollment in the study. Patients with impending respiratory failure will not be approached for enrollment. Once enrolled, patients will be randomized to receive aerosol therapy via JN with AM or MP (control group) or VMN with VM or MP (study group). Randomization process will consist of numbering 220 envelopes from 1-220 (110 for each arm). Using a simple randomization method each numbered envelope will be assigned to study or control group with a corresponding card placed inside indicating JN or VMN. Envelopes will then be sealed and held by PI. Envelopes will be assigned to study subjects in numerical order. Mask or mouthpiece selection will be made based on patient's age and/or ability to comply with using a mouthpiece. Patients will be treated according to CMCED's AACPA with the following modifications to allow for blinding and data collection:

Phase 1a (1st hour)

- According to AACPA initial treatment consists of three β-agonist treatments (albuterol & Ipratropium), which can be delivered in 20-minute increments or combined and given continuously over one hour. For blinding and assessment purposes 3 intermittent treatments will be given instead of continuously for this study.
- Two study personnel will be used to provide treatment:
 - One will administer all treatments with assigned nebulizer, perform pre-study assessments and note the start time of the treatment. Once aerosol treatments are completed the assigned nebulizer will be placed in a non-transparent bag for blinding.
 - The second "blinded" study personnel will perform post assessment and assign an AS.
- Since JN and VMN aerosolization rates differ, post assessment by blinded study personnel will not occur until 20 minutes has elapsed from initiation of treatments.
- Patients will receive an AS after each treatment and will be treated accordingly.
- If after the 1st treatment a patient receives an AS of 1-4 (mild) they will be treated according to the "mild" pathway.
- If patients receive an AS of 5-12 (moderate to severe) they will receive their 2nd treatment and/or 3rd treatments.
- Patients will continue to be assessed and scored every 20 minutes regardless of AS.
- This procedure will be repeated until all 3 three treatments and/or assessments are completed in Phase 1a of AACPA.

- Once patients have finished treatments in Phase 1a they will either move to Phase 1b, be discharged or be admitted per AACPA guidelines.
- For consistency in CMCED length of stay and discharge criteria patients will be monitored for 40 minutes after their last treatment before discharge orders.
- If at any time or any Phase, the patient is deemed to be in impending respiratory failure by treating physician, they will be removed from the study and be treated according to physician orders.

Phase 1b (2nd hour)

- Treatments will be administered in the same fashion as Phase 1a with their assigned nebulizer.
- If an additional hour long treatment is ordered per AACPA, 3 intermittent treatments given in 20 minute increments will be administered in the same manner as Phase 1a.
- Once patients have finished treatments in Phase 1b they will either move to Phase 1c, be discharged or admitted per AACPA guidelines.

Phase 1c (3rd hour)

- If patients advance to Phase 1c, they will receive subsequent aerosol treatments and assessments in the same manner until they are either (1) admitted to hospital, or (2) discharged from CMCED per AACPA guidelines/pathway.
- If continuous bronchodilator treatment is ordered per AACPA in Phase 1c then study procedure will stop and patient will be treated per standard practice using large volume jet nebulizer.

5. Sub-Study Procedures:

N/A

6. Criteria for Inclusion of Subjects:

2 to 18 year old (up to 19th birthday) otherwise healthy children with primary diagnosis of acute moderate to severe exacerbation of asthma presenting to Children's Medical Center Emergency Department, Dallas.

7. Criteria for Exclusion of Subjects:

- Children < 2 years old
- Children with comorbid/complex medical conditions such as: congenital or acquired cardiovascular disease, cystic fibrosis, chronic lung disease (other than asthma), bronchopulmonary dysplasia, airway anomalies (e.g., tracheomalacia) or immunodeficiency syndromes.
- Patients with coexisting medical condition such as pneumonia
- Patients in impending respiratory failure as determined by treating physician
- Patients that have had oral corticosteroids within 24hrs of CMCED admission
- Patients that have had bronchodilator treatment within one hour of CMCED admission

8. Sources of Research Material:

Electronic medical record (EMR) will be used to collect data regarding vital signs (HR, RR, SpO₂), breath sounds, work of breathing, and asthma scores. Additional data collected from EMR and used for analysis will be demographics, diagnosis, previous medical history, medication dosages, number of treatments administered, and time in CMCED. Other data not collected in EMR will be recorded on case report forms (CRFs) and entered into a secure password protected EXCEL spreadsheet. Data collected on CRFs will include nebulizer used for treatment based on randomization, type of interface used for treatment (AM, VM, MP), bronchodilator use prior to CMCED admission, oral corticosteroid administration pre/post CMCED admission, patient tolerance/compliance with aerosol treatment, as well as any adverse side effects.

9. Recruitment Methods and Consenting Process:

Study personnel will screen CMCED census through the EMR for patients diagnosed with acute asthma exacerbation and an initial assessment of moderate to severe asthma (AS 5-12), per the AACPA. Patients that have an existing treatment relationship with Co-Investigator Physician might also be approached for enrollment. Study personnel will approach the parents for study consent as soon as possible after CMCED admission and before any bronchodilator treatment begins. Enrollment will be available only to Spanish and English speaking families due to availability of translation services; a translator will be utilized for consent and documentation purposes for Spanish speaking families only. The expected duration of this study is 3-4 months.

10. Potential Risks:

- 1) Loss of Confidentiality**
- 2) Delivery of inhaled Short-Acting Beta₂-Agonists, in general, cause few systemic adverse effects[4]:
 - Tachycardia
 - Skeletal muscle tremor
 - Hypokalemia
 - Increased lactic acid
 - Headache
 - Hyperglycemia

11. Subject Safety and Data Monitoring:

Patient's well-being and medical status will be monitored by CMCED staff throughout their emergency department stay in line with current standards of care and according to the AACPA. Vital signs will be monitored pre and post each aerosol treatment. If a vital sign is noted to be abnormal or an adverse event occurs, the RT or nurse for that patient will notify treating physician and PI. There will be a written report created of any adverse events that occur during treatments and a report will be made to the PI and the PI's faculty sponsor within 24 hours. Any reported adverse events will be reviewed at the time they are reported to determine if the adverse event was in any way caused by the study procedure. Any events deemed due to the study procedure will cause the study to be halted and further reviewed. Changes to the study procedure will be made as needed and reported to the IRB. The study will resume upon approval. Data will also be reviewed weekly by PI and co-investigator for any trends in safety concerns.

12. Procedures to Maintain Confidentiality:

To protect subject confidentiality, all data will be kept in a password-protected Excel database and all hard copies of data case report forms will be stored in a locked filing cabinet within PI's badge access restricted office. Only PI will have key to locked cabinet. Subjects will be given a study identification number, and patient identifiers will not be included in the database or hard copies of files. No patient name or identifying information will be included in any dissemination of study findings. The master list that links patient identifiers to the study subject will be kept recorded in a secure password protected EXCEL spreadsheet and paper copy under lock at the Pls office. It will be made very clear during the consent procedure that the patient/legal guardian will be free to withdraw from the study at absolutely any time, for any reason. Upon completion of data collection, all PHI will be de-identified. Only the study team will have access to study records and data. If a patient revokes authorization for participation in the study, all data will be discarded and will not be used. Data will be collected during the study days, specifically for purpose of the study

13. Potential Benefits:

Potential benefits derived from use of VMN for research subjects are:

- Decreased treatment times
- Fewer overall treatments
- Decreased time in Emergency Department
- Decreased admissions
- Decreased medication dosages

Potential benefits derived from use of VMN to others with similar problems are:

- Decreased treatment times
- Fewer overall treatments
- Decreased Emergency Department and/or primary care physician visits
- Decreased hospital admissions
- Decreased medication dosages
- Better control of symptoms and/or exacerbations

Potential benefits to society derived from use of VMN are:

- Decreased healthcare costs
- Decreased Emergency Department utilization

14. Biostatistics:

Original Power/Sample Size Calculation

Based on a comparable study[11], the hospital admission rate is estimated to be 60% in the jet nebulizer group and 33% in the vibrating mesh nebulizer group, respectively. A sample size of 60 patients per group (120 patients in total) will achieve 80% power to detect statistically significant difference in hospital admission rates between the two groups (significance level=0.05, 2-sided).

Blinded Interim Power Analysis

At 108 patients a blinded interim power analysis revealed the rate of hospitalization is 20/108 or 18.5%. This is considerably lower than the rates anticipated in the original design. This is an indication that either the study population is much different than the population in the referenced work or the implementation of the intervention is different in this study. The overall rate of admission was around 45% in the referenced work. As an estimate of the effect of the intervention, maintaining something similar to a 2 to 1 admission rate between arms, this would indicate the comparison will be between one arm with a 12.5% admission rate and a second arm with a 27.5% admission rate. The same power calculation as before is repeated here for the lower rates which are more in line with what is being observed. This indicates that the shift in rates does have an impact on the power of the study. The study would require 220 subjects to still have 80% power to detect the difference. At the current sample size of 120, the study only has 53.8% power.

1. Shrestha, M., et al., *Continuous vs intermittent albuterol, at high and low doses, in the treatment of severe acute asthma in adults*. Chest, 1996. **110**(1): p. 42-7.

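### Does the number of treatments need a fixed counting unit because continuous therapy in Phase 1c is not converted into three treatments?

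*Combined protocol and SAP*

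**What the plan says.** Section 3 (Concise Summary of Project) states: "Secondary study outcomes will be number of treatments and length of stay in CMCED". Section 1 includes fewer treatments in the hypothesis. Section 8 lists the data item among those drawn from the electronic record: "number of treatments administered, and time in CMCED". Section 14 (Biostatistics) deals only with hospital admission.

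An hour of therapy is described in four places:

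- Section 2 (Background), on general recommendations for three treatments in an hour: "in 20 minute increments or one treatment continuously over an hour".
- Section 4, Phase 1a, on the pathway's three initial treatments: "which can be delivered in 20-minute increments or combined and given continuously over one hour". The study gives them intermittently.
- Section 4, Phase 1b: "If an additional hour long treatment is ordered per AACPA, 3 intermittent treatments given in 20 minute increments will be administered".
- Section 4, Phase 1c: "If continuous bronchodilator treatment is ordered per AACPA in Phase 1c then study procedure will stop". The patient then receives standard care by large volume jet nebulizer, whichever arm they are in.

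Two other rules in Section 4 touch the secondary outcomes. Patients judged to be in impending respiratory failure leave the study: "they will be removed from the study and be treated according to physician orders". For length of stay: "For consistency in CMCED length of stay and discharge criteria patients will be monitored for 40 minutes after their last treatment before discharge orders".

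**The concern.** Read together, these passages seem to give the same hour two values. The Background calls it one treatment, Phase 1a calls it three combined, and Phase 1b turns one order into three administrations. In Phase 1c the conversion stops, and only for patients who still need escalation in the third hour.

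If that hour is left out or entered as one administration, an escalated patient can show fewer treatments than a patient who stayed on intermittent therapy. Switching follows randomization and depends on response, so it could differ between arms. If jet nebulizer patients switched more often, a plain count would hide part of any advantage of the mesh nebulizer. With 0, 1 and 3 all arguable, a unit chosen after unblinding could move the result. Length of stay raises a smaller version of the worry: no start or end of the clock is written, and the 40-minute rule applies only to discharged patients.

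**Working it through.** **The plan's own conversion.** 60 minutes / 20 minutes = 3 treatments per hour, as in Phase 1b.

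**Per patient.** With 3 treatments in Phase 1a and 3 in Phase 1b, the count is 6. One continuous hour then gives 6 + 0 = 6, 6 + 1 = 7 or 6 + 3 = 9. The comparator of 9 for a patient who stays intermittent is an assumption, because the plan gives no number of treatments for Phase 1c.

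**Between arms.** Relative to a count of 3:

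shift in the jet-minus-mesh difference = -k × (switch share, jet - switch share, mesh), per continuous hour, with k = 3 - 1 = 2 or k = 3 - 0 = 3.

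The switch shares below are assumptions, since the documents give none.

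| Jet vs mesh | Hour counted as 1 | Hour counted as 0 |
|---|---|---|
| 10% vs 5% | -0.10 | -0.15 |
| 20% vs 10% | -0.20 | -0.30 |
| 27.5% vs 12.5% (every admitted patient switched) | -0.30 | -0.45 |
| 10% vs 10% | 0 | 0 |
| 5% vs 10% | +0.10 | +0.15 |

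The sign follows whichever arm switches more.

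**Does it cost power?** Assume SD 2 on the count-3 scale, 110 per arm, and switches equal to half of admissions at the planning rates of 27.5% and 12.5%, that is 13.75% vs 6.25% (average 10%).

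- SE = 2 × √(2/110) = 0.270. Difference detectable with 80% power = (1.960 + 0.842) × 0.270 = 0.756.
- Shift = 0.075 × 2 = 0.150 or 0.075 × 3 = 0.225, leaving 0.606 or 0.531.
- With SD held at 2, power is 61% or 50%.

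Holding the SD fixed is not coherent, because the recount lowers the highest counts. Put switchers at 9 on the count-3 scale and non-switchers at an assumed mean m of 3 to 5. Then:

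variance after recount = 4 - 0.10 × 0.90 × (9 - m)² + 0.10 × 0.90 × (9 - k - m)².

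| m | Count | Variance | SD | SE | Difference / SE | Power |
|---|---|---|---|---|---|---|
| 3 | 1 | 4 - 3.24 + 1.44 = 2.20 | 1.48 | 0.200 | 3.03 | 86% |
| 5 | 1 | 4 - 1.44 + 0.36 = 2.92 | 1.71 | 0.230 | 2.63 | 75% |
| 3 | 0 | 4 - 3.24 + 0.81 = 1.57 | 1.25 | 0.169 | 3.14 | 88% |
| 5 | 0 | 4 - 1.44 + 0.09 = 2.65 | 1.63 | 0.220 | 2.42 | 68% |

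On the same inputs, power may fall modestly or rise. Every input except the 110 per arm and the two admission rates is assumed, so none of these powers is an estimate for this trial.

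**Length of stay.** If all non-admitted patients are discharged under the 40-minute rule, it adds 40 × 0.725 = 29 minutes to one arm's mean and 40 × 0.875 = 35 to the other's, a difference of 6 minutes.

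**The case for a change.** The strongest case for a change is that the ambiguity lies within the study procedures and not only in the Background: Phase 1b turns one ordered hour into three administrations, and Phase 1c does not. Escalation depends on response, so the arms may differ, and the record may hold a long continuous administration as a single entry. A counting rule would cost one sentence and would remove a choice that could otherwise be made with the results in view.

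Part of this stands. No passage says whether, or in what unit, therapy after a Phase 1c stop enters the count, and a count of 0 or 1 can rank an escalated patient below one who was not escalated.

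The rest does not hold. The Background and Phase 1a wording describes ways of giving care and does not define an outcome unit. The three-for-one replacement governs what is given with the assigned device in Phases 1a and 1b. Phase 1c is a different event: the study procedure is over and both arms receive the same standard device. To say that a plain count understates treatment presumes that 3 is the true value, and that is a convention statisticians could reasonably dispute. The claim that the direction is known depends on unknown switch rates. The clinical pathway is not reproduced in the protocol, so continuous therapy might coincide with admission, leaving little or no emergency department time to miscount. Section 8 also collects medication dosages, which gives a separate record of treatment intensity.

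**Conclusion.** No change follows. This is an unwritten detail of one secondary outcome, of a kind that analysts fill sensibly when they define the variable. Within the study procedure treatments are discrete and countable. Whoever builds the dataset will have to decide how to enter continuous therapy and can show the other choice alongside it.

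The effect is 2 or 3 treatments per switched hour for an individual, and 0.10 or 0.15 in the mean difference per 5-point imbalance in switching. It is zero if the arms switch equally and reverses if the mesh arm switches more. These figures rest on one continuous hour per switch and on three treatments as its equivalent, neither of which the documents establish for Phase 1c. No figure for lost power should be relied on.

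The length-of-stay point is worth at most about 6 minutes through the 40-minute rule, and time in the department is already recorded. Removal for impending respiratory failure is a question of which patients are analysed and does not bear on the counting unit. The admission outcome and its sample size are untouched.

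### Section 3 says investigators are blinded to the nebulizer, but the record handling in Sections 8, 11 and 12 does not blind the PI

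*Combined protocol and SAP*

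**What the plan says.** Section 3 makes the blinding claim for two groups and exempts nobody: "Investigators and treating physicians will be blinded to which nebulizer was assigned to each patient".

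Four other sections bear on whether the PI can be blinded:

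- **Section 4** describes numbered envelopes, each "with a corresponding card placed inside indicating JN or VMN". On custody it says: "Envelopes will then be sealed and held by PI".
- **Section 8** says: "Data collected on CRFs will include nebulizer used for treatment based on randomization". The same form takes the interface (AM, VM or MP), tolerance and adverse side effects. CRF data are then entered in a password-protected spreadsheet.
- **Section 12** keeps the paper CRFs in a cabinet in the PI's office and adds: "Only PI will have key to locked cabinet". Records and data are open to the study team, with no division into blinded and unblinded members.
- **Section 11** has abnormal vital signs and adverse events notified to the PI, with a written report to the PI and the faculty sponsor within 24 hours. Each event is reviewed for whether the study procedure caused it, and an event so judged halts the study. It also says: "Data will also be reviewed weekly by PI and co-investigator for any trends in safety concerns".

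**The concern.** A blinding statement is useful only if some procedure keeps the allocation from the people it names. Here the person with the most complete access to the records is an investigator, and those records name the device.

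What is exposed is judgement about safety. Whether an adverse event is due to the study procedure is a subjective call, and it can stop the trial. A reader of Section 3 would take that call, and the weekly look for safety trends, to be made without knowledge of the device. If they are not, the report would claim a protection that the trial did not have.

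**Working it through.** No arithmetic applies. The check is which records identify the arm, who can reach them, and what masking step stands in between.

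1. **What identifies the arm.** The envelope card does, and so does the nebulizer field on the CRF. The interface field does so in part. Under Sections 3 and 4, AM is used only in the control arm and VM only in the study arm, while MP is used in both. The nebulizer field therefore reveals the arm for every patient, and the interface field reveals it for every patient treated by mask. Removing the nebulizer field alone would not mask the file.

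2. **Envelopes.** They are sealed, and "Envelopes will be assigned to study subjects in numerical order". The plan does not say who prepared the sequence, who opens each envelope, or where opened cards go. Holding a sealed envelope is not knowing its content. This is a weakness in the description of concealment and does not show unblinding.

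3. **CRFs and spreadsheet.** The paper forms carry both fields and the PI alone has the key. The spreadsheet receives CRF data, and no section says that either field is withheld or coded. The PI's access is thus part of the written procedure.

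4. **Use of the records.** Adverse side effects are recorded on the same CRF as the nebulizer and interface, so reading that form for safety puts the arm in view. Vital signs and asthma scores come from the EMR, so a review limited to those need not show the device. The plan does not say which fields the weekly review uses, or who makes the causality judgement.

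5. **Masking steps that do exist.** Section 4 gives a second, blinded person for the post-treatment score, a wait until 20 minutes have passed from the start of treatment, and an opaque bag for the used nebulizer. All three act at the bedside. None limits an investigator's access to records.

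| Role | What the documents show |
|---|---|
| Treatment-giver | Unblinded by design |
| PI | Access to both identifying fields; no masking step described |
| Co-investigator | Joins the weekly review, fields unspecified; unblinding possible, not established |
| Second assessor | Bedside safeguards in place; not shown to be unblinded |
| Treating physicians | Said to be blinded; not shown to be unblinded |

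**The case against.** The strongest reply is that the blinding that matters for the primary outcome is intact. Disposition follows the AACPA, and the post-treatment scores come from a blinded assessor. The PI is a respiratory therapist and research coordinator to whom no section gives an admission decision. A weekly review will usually come after the patient has left the department, and knowing earlier patients' devices does not open the next sealed envelope. The review may also be run on EMR data without the device. Most of this stands, and it confines the point to the PI and to safety judgements. The last part does not fully answer it: a review without the device field is possible, but the plan does not call for one, and adverse effects sit on the device-bearing form.

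Three stronger readings are tempting, and the documents do not support them.

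- *The co-investigator could sway admissions.* Section 9 says: "Patients that have an existing treatment relationship with Co-Investigator Physician might also be approached for enrollment". That sentence concerns recruitment. It does not say that this physician decides disposition in the emergency department, or knows the device when doing so.
- *The sample size increase was made with knowledge of arm results, so type I error is inflated.* Section 14 calls the analysis blinded, reports only a pooled 20/108 (18.5%), and bases the increase on the low overall rate and an assumed ratio of about 2 to 1. It describes no test between arms. An error rate computed for an unblinded look would describe a procedure that is not in the plan.
- *The trial has no effective blinding.* The bedside measures protect the asthma score, and nothing here undoes them.

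**Conclusion.** The claim of investigator blinding does not hold for the PI as the plan is written. Sections 8 and 12 give the PI device-labelled records, and no section describes a step that would mask them. The safety and causality judgements in Section 11 therefore cannot be assumed blind to device.

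The conclusion rests on two readings: that the PI counts as an investigator under Section 3, and that where no masking is described, none is planned. An unwritten masking practice would answer the point once it was documented.

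No numerical size can be given. Any bias depends on who judges causality and what that person sees, and the documents state neither. The plan's sample size and power figures do not depend on this point. It calls for a correction to the plan and the report, and does not show that the admission comparison is biased.

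**What to change.** Have the treatment-giver, who is already unblinded, record nebulizer and interface in a separate log. Keep that log apart from the PI-held CRFs, and leave both fields out of the spreadsheet used for the weekly review and the first causality judgement. Both must go, because the mask type alone reveals the arm. Allow unmasking when a safety signal needs it, and document each occasion.

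If this is not done, delete investigators from the blinding statement in Section 3 and report that the PI had access to allocation. The same disclosure is needed for patients already enrolled under the present arrangement, since a split log cannot change what was accessible before.

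The cost is a short amendment and one additional log, with no extra staff. The downside is small: a safety reviewer must ask for unmasking before seeing the device. An independent holder for the remaining envelopes would tighten concealment, but may need another person and is not required to resolve this point.

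### Treating physicians are declared blinded, but no step hides the device from them during treatment, and the bagging rule does not cover the arm-specific mask

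*Combined protocol and SAP*

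**What the plan says.** **Blinding claim and outcome (Section 3, Concise Summary of Project).** "Investigators and treating physicians will be blinded to which nebulizer was assigned to each patient". Shortly afterwards: "Primary study outcomes will be hospital admission rates".

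**Concealment (Section 4, Phase 1a).** "Once aerosol treatments are completed the assigned nebulizer will be placed in a non-transparent bag for blinding". The sentence names the nebulizer only.

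**Other blinding measures (Section 4, Phase 1a).** One person gives the treatments. The second, blinded "study personnel will perform post assessment and assign an AS". That score waits until 20 minutes after the start, because the two devices aerosolize at different rates. Intermittent treatments replace the continuous option, partly for blinding.

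**Interface.** Section 1 compares the jet nebulizer (JN) with aerosol mask (AM) or mouthpiece (MP) "versus a vibrating mesh nebulizer (VMN) with a valved-mask (VM) or MP". Sections 3 and 4 repeat this pairing. The choice between mask and mouthpiece depends on age and ability to comply.

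**Use of the score and the physician's part (Section 4).** "Patients will receive an AS after each treatment and will be treated accordingly". Movement between phases, discharge and admission follow the emergency department's asthma pathway (AACPA). A child "deemed to be in impending respiratory failure by treating physician, they will be removed from the study", at any time and in any phase.

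**The concern.** The blinding of treating physicians is a stated safeguard for the trial, but the procedures in Section 4 do not provide it. A physician who enters during a treatment sees the device. A physician who enters afterwards may still see the mask, because the protocol does not say what happens to it. For a child using a mask, the type of mask is enough to identify the arm.

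The study hypothesis is that the mesh nebulizer leads to fewer admissions. If the physician has discretion in borderline cases and knows the arm, that expectation can act in one direction. The result would be bias in the primary comparison, which a larger sample does not remove. The same knowledge could affect the judgement that takes a child out of the study.

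**Working it through.** **Step 1. Whom does each blinding measure protect?**

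| Measure (Section 4, Phase 1a) | Protects the scorer | Hides equipment from the physician |
|---|---|---|
| Separate blinded scorer | Yes | No |
| 20-minute hold before scoring | Yes, masks differing run times | No |
| Intermittent treatments | Yes, creates scoring windows | No |
| Bagging the nebulizer after treatment | Yes, for the nebulizer | After treatment only, nebulizer only |

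Phases 1b and 1c repeat the Phase 1a procedure, so they add no further concealment.

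**Step 2. What does the interface reveal?** AM appears only with JN, VM (valved mask) only with VMN, and MP with both. A visible mask identifies the arm. A visible mouthpiece does not. The documents do not give the share of children using a mask.

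**Step 3. How large could the effect be?** The plan gives no figure for blinding, so this is an illustration.

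Inputs from Section 14: two-sided significance level 0.05; blinded admission rate 20/108 = 18.5%; revised rates 12.5% and 27.5%, a target difference of 15 points. From Section 4: 110 per arm.

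Formula (two-proportion z-test with pooled variance), for a gap d centred on p̄, with p1 = p̄ + d/2 and p2 = p̄ − d/2:

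- SE0 = √(2·p̄(1−p̄)/n)
- SE1 = √([p1(1−p1) + p2(1−p2)]/n)
- P(reject) = Φ((d − 1.96·SE0)/SE1) + Φ((−d − 1.96·SE0)/SE1)

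*Check against the plan's figures.* With p̄ = 0.20 and d = 0.15:

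- n = 60: SE0 = 0.0730, SE1 = 0.0717, first argument 0.096, power 53.8%. The plan states 53.8%.
- n = 110: SE0 = 0.0539, SE1 = 0.0530, first argument 0.836, power 79.8%. The plan states 80%.

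The formula reproduces both.

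*Illustration.* Take no true effect, p̄ = 0.185 and n = 110, so SE0 = 0.0524. Let d be the gap produced solely by knowledge of the arm. The gaps are assumptions.

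| Assumed gap over all 220 | p1, p2 | SE1 | Arguments of Φ | False-positive rate |
|---|---|---|---|---|
| 0 | 18.5%, 18.5% | 0.0524 | −1.960, −1.960 | 5.0% |
| 3 points | 20%, 17% | 0.0523 | −1.388, −2.535 | 0.083 + 0.006 = 8.8% |
| 5 points (5/15, one third of the target) | 21%, 16% | 0.0522 | −1.007, −2.921 | 0.157 + 0.002 = 15.9% |

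*If only mask users are affected.* Assume that half the children use a mask. A 3-point gap among them is then 0.5 × 3 = 1.5 points overall, and the rate is 5.9%. A 5-point gap among them is 2.5 points overall, and the rate is 7.6%. This dilution applies to exposure through the mask. A nebulizer seen in use can reveal the arm for mouthpiece users too.

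**The case against.** The case for the plan has several sound parts.

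- **Bagging is not the only blinding measure.** The separate scorer, the 20-minute hold and intermittent dosing are deliberate and useful. This stands, but all three protect the scorer, and none hides equipment from the physician.
- **Bagging takes place in each cycle.** A reader might infer from the plural in the bagging sentence that the nebulizer stays in view until all treatments are over. The documents do not support that: Section 4 says that the procedure is repeated until the treatments and assessments of Phase 1a are finished, which points to bagging each time.
- **The protocol does not say that the mask stays in view.** A reader might infer that following the text unmasks every mask user. The text is silent on the mask, so its handling is undefined. Staff may well remove it with the nebulizer.
- **The protocol does not say that the physician decides admission.** Admission follows the AACPA, fed by a blinded score. The pathway is not in the documents, so the room for discretion is unknown. The one physician judgement stated for the study course is impending respiratory failure.
- **The size is hypothetical.** The documents give neither the shift, nor its direction, nor the mask share.

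One gap survives all of these: physician blinding is asserted, and no procedure delivers it while treatment is in progress.

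**Conclusion.** The point holds as a gap between a stated property and the procedures meant to secure it. Followed as written, Section 4 does not keep the treating physician from seeing the device in use, and it leaves the arm-specific mask unaddressed.

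Bias in the primary outcome is possible but not demonstrated. It requires that the physician has some discretion over admission and learns the arm. Under assumed gaps of 3 and 5 points across all 220 children, the false-positive rate would be about 9% and 16% instead of 5%. If only mask users were affected and they were half the sample (also an assumption), it would be about 6% and 8%. The change is worth making because it is cheap and concerns the primary outcome.

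**What to change.** 1. **Bagging rule, Section 4.** After each treatment, in every phase, the nebulizer and its mask or mouthpiece are both removed and bagged before the blinded scorer or the treating physician sees the child.
2. **Treatment in progress.** Choose one. Either the physician's routine, non-urgent assessments take place after bagging, and the case report form (CRF) records any occasion on which the physician saw the device in use; or the Section 3 claim is limited to the post-treatment scorer. Bagging alone does not close this gap.
3. **Admission decision.** State who makes it under the AACPA.
4. **Optional.** A CRF item for the physician's guess of the device may be added as description only. At disposition the guess is mixed up with the child's response, so it should not decide whether the blinding claim stands.

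The cost is a few sentences, a few seconds per treatment and, under the first option in item 2, one CRF item and some coordination of when the physician visits. The change covers only children enrolled after it. At least 108 were already enrolled at the interim power analysis, and the trial report should say so.
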